5.1 Description of the Overall Trial Design and Plan

5.1.1 Trial Design

This will be a multicenter, observer-blind, controlled, randomized, Phase II study. A total of 320 subjects aged 18 to <65 years will be included. Each subject will receive one of the 2 formulations of the Purified Vero Rabies Vaccine - Serum Free (VRVg) or the Rabies Human Diploid Cell Vaccine Imovax Rabies. Vaccination will be according to the ESSEN post-exposure schedule (i.e., a total of 5 injections [1 injection per day] administered at D0, D03, D07, D14 and D28) and human rabies immunoglobulins (HRIG) will be administered at D0.

Subjects will be assigned to the VRVg-1 group, VRVg-2 groups or Imovax Rabies group as presented in the table below.

Table 5.1 Distribution of Subjects According to Vaccination Group

	Vaccine	Formulation	Dosage	Number of subjects
Group 1	VRVg	VRVg-2	Low	80
Group 2			Medium	80
Group 3			High	80
Group 4		VRVg-1		40
Group 5	Imovax® Rabies			40

All subjects will provide blood samples before the first vaccination at D0 (baseline titer) and for the assessment of the immune response to the rabies vaccine at D14, D28, D42 and at M7.

Safety will be assessed in all subjects during the vaccination period and up to 28 days after vaccinations, in terms of occurrence of AEs, SAEs and adverse events of special interest (AESIs). In addition, SAEs and AESIs will be collected up to 6 months after the last vaccination in all subjects.

[figure not shown]

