3.1 Trial Design

This will be a multicenter, observer-blind, controlled, randomized, Phase II study.

A total of 320 subjects aged 18 to <65 years will be included in the study.

Each subject will receive one of the 2 formulations of the Purified Vero Rabies Vaccine - Serum Free (VRVg) or the Rabies Humain Diploid Cell Vaccine Imovax Rabies. Vaccination will be according to the ESSEN post-exposure schedule (i.e., a total of 5 injections [1 injection per day] administered at D0, D3, D7, D14 and D28) and human rabies immunoglobulins (HRIG) will be administered at D0. Subjects will be assigned to the VRVg-2 groups (low, medium and high dosage), VRVg-1 group, or Imovax Rabies group with a 2:2:2:1:1 allocation ratio..

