5.1.1.2 Statistical Methods

5.1.1.2.1 Immunogenicity

The descriptive immunogenicity analysis at D0, D14, D28, D42 and M7 will be performed to document immunogenicity of the 5 groups.

5.1.1.2.1.1 Descriptive Immunogenicity

For all the subjects, a descriptive analysis for pre dose 1 (D0), pre dose 4 (D14), pre dose 5 (D28), 14 days post dose 5 (D42) and 6 months after the last injection (M7) will present the following statistics for the rabies virus neutralizing antibody (RVNA) titers in each randomized vaccine group:

- Number of subjects with RVNA titer available
- Number and percentage of subjects with RVNA titer ≥ 0.2 (LLOQ) IU/mL and 95% CI of the proportion
- Number and percentage of subjects with RVNA titer ≥ 0.5 IU/mL, and 95% CI of the proportion
- Number and percentage of subjects with complete neutralization at the starting dilution (1/5) of the RFFIT assay
- GMTs and 95% CI of RVNA titers
- GM of individual titer ratio (GMTR):
 - D14/D0
 - D28/D0
 - D42/D0

- M7/D0
- Distribution of titers (minimum, Q1, median, Q3, maximum)
- Log₁₀: mean and its standard deviation (SD)
- Ratio of GMT at D14, D28 and D42 between:
 - Each VRVg group (VRVg-2 low, medium and high dosages and VRVg- 1 group) versus Imovax® Rabies
 - Each VRVg-2 group (VRVg-2 low, medium and high dosages) versus VRVg-1
 - VRVg-2 medium and high dosages versus low dosage
 - VRVg-2 high dosage versus medium dosage

The lower and upper limits of the two-sided 95% CIs of the proportions will be computed using the exact binomial method (Clopper-Pearson method) (1). For the ratio of GMTs between VRVg and Imovax® Rabies, the 95% CI will be obtained by antilog back-transformations of the CI of the difference [log₁₀(GMT VRVg)-log₁₀(GMT Imovax Rabies)] obtained using the usual calculation for normal distribution.

The complete descriptive immunogenicity data will be analyzed according to randomization group in FAS population. The main parameters, defined as GMTs and percentages of subjects with titers ≥ 0.5 IU/mL will also be described on the PP population.

Additionally, RCDC will be plotted in all vaccine groups, at D0, D14, D28, D42 and M7. Boxplots and density distribution of RVNA titers at D14, D28 and D42 will also be produced. All these figures will be plotted on the FAS population.

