5.1.3 Exploratory analyses

5.1.3.1 5.1.3.1 Immunogenicity

5.1.3.1.1 Descriptive immunogenicity in the subset of subjects with a baseline titer < 0.5 IU/mL

In case more than 5% of subjects in the FAS (all vaccine groups) have a baseline titer ≥ 0.5 IU/mL, a descriptive analysis of immunogenicity parameters (GMT and percentage of subjects with a titer >0.2 IU/mL at D0, D14, and D42) will be provided on the subset of subjects with a baseline titer <0.5 IU/mL. This descriptive immunogenicity analysis will be performed according to the randomized vaccine on the FAS population.

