5.2.2 Per-Protocol Analysis Set

The per-protocol (PP) analysis set is a subset of the full analysis set (FAS).

The PPAS will be defined based on the D14 timepoint (in healthy individuals who are vaccinated, the 0.5 IU/mL threshold considered to be protective should be achieved in most individuals by day 14 after the first injection of a post-exposure regimen, with or without simultaneous administration of rabies) (2).

The subjects presenting with at least one of the following relevant protocol deviations before D14 (i.e. 7 days after the third vaccine injection) will be excluded from the PPAS:

- Subject did not meet all inclusion protocol-specified inclusion criteria or met at least one of the protocol-specified exclusion criteria
- Subject did not receive the correct number of the first three doses of vaccine
- Subject received a vaccine other than the one that he/she was randomized to receive for the first three doses of vaccine
- Preparation and/or administration of vaccine was not done as per protocol for the first three vaccinations
- Subject did not receive 2nd and 3rd vaccines in the proper time window from D0, as follows:
 - Vac2 in [D3-D5]

- Vac3 in [D7-D9]
- Subject did not provide a post-dose 3 serology sample in the proper time window [D13-D15] from D0
- Subject received a protocol-restricted therapy/medication/vaccine (belonging to category 2) from D0 to D14
- Subject's serology sample is missing or did not produce valid test results at both D0 and D14
- Seropositive subject at D0, i.e. RVNA titer \geq LLOQ
- Subject developed a protocol-specified withdrawal criterion from D0 to D14 but was not withdrawn
- Subject did not receive the correct amount of Imogam at D0
 - Outside the +/-10% the theoretical calculated volume

The PP analysis set will be defined at D14. Adherence to the definition of the PP analysis set may be decided during a blind-review of data, i.e. before breaking the code. Subjects in the PP analysis set will be analyzed according to the vaccine received.

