5.5 Determination of Sample Size and Power Calculation

An arbitrary number of 80 subjects per VRVg-2 group and 40 subjects in both VRVg-1 and Imovax Rabies has been proposed.

Table 5.4:

In terms of safety, according to the occurrence rate of the observed AEs, 80 subjects will allow for the following 95% CI (Table 5.5).

95% CI calculations corresponding to anticipated AEs rates in VRVg-2 groups of 80 subjects.

Table 5.5: 95% CI calculations corresponding to anticipated AEs rates in VRVg-2 groups of 80 subjects

| Observed numbers | Observed % | 95% CI |
|------------------|------------|--------------|
| 8/80 | 10.0 | (4.4; 18.8) |
| 12/80 | 15.0 | (8.0; 24.7) |
| 16/80 | 20.0 | (11.9; 30.4) |
| 20/80 | 25.0 | (16.0; 35.9) |
| 24/80 | 30.0 | (20.3; 41.3) |

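### The planned between-group GMT ratios ignore the D0 titer that every subject provides; adding D0 serostatus would be a free, optional gain in precision

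*SAP*

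**What the plan says.** Protocol 5.1.1 makes D0 RVNA universal: "All subjects will provide blood samples before the first vaccination at D0 (baseline titer"). The synopsis places that sample before both vaccine and HRIG, so D0 is a clean pre-treatment value.

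SAP 5.1.1.2.1.1 lists the "Ratio of GMT at D14, D28 and D42 between" pairs of groups: four VRVg groups against Imovax Rabies, three VRVg-2 dosages against VRVg-1, and three comparisons among the dosages, ten in all. For the ratios against Imovax Rabies, "the 95% CI will be obtained by antilog back-transformations of the CI of the difference" of log10 GMTs by the usual normal-theory calculation. The full set of statistics is run on the FAS by randomized group.

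The per-protocol repeat is narrower: "The main parameters, defined as GMTs and percentages of subjects with titers ≥ 0.5 IU/mL will also be described on the PP population". The PPAS (SAP 5.2.2) excludes any "Seropositive subject at D0, i.e. RVNA titer" at or above LLOQ, which Protocol 9.1.2 sets at 0.2 IU/mL. SAP 5.1.3.1.1 adds a conditional table: if more than 5% of the FAS have a D0 titer of 0.5 IU/mL or more, GMTs and the percentage above 0.2 IU/mL at D0, D14 and D42 "will be provided on the subset of subjects with a baseline titer <0.5 IU/mL".

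The covariates explored in SAP 5.1.3.1.2 are gender, age group, race and center. D0 titer is not among them.

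**The concern.** Eligibility excludes reported rabies vaccination, recent immune globulins or blood products, and high risk of rabies infection during the trial (Protocol 5.2.5). There is no serological screen (Protocol 5.2.3), so a subject with existing RVNA can be randomized. Such a subject may show a recall response well above that of naive subjects. With arms of 40 and 80, a few of them falling unevenly would move a GMT ratio and enlarge its variance for reasons unrelated to dosage.

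The SAP handles this in the PPAS and in the conditional subset, but neither yields a between-group ratio. The GMT ratios are the only between-group immunogenicity estimates listed, in a trial whose purpose is to choose a dosage. The variable needed to remove this noise is already collected.

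**Working it through.** **Inputs from the documents.** SAP 5.5: "An arbitrary number of 80 subjects per VRVg-2 group and 40 subjects in both VRVg-1 and Imovax Rabies has been proposed"; SAP 3.1: "with a 2:2:2:1:1 allocation ratio". So 320 splits into 80/80/80/40/40. The trigger in SAP 5.1.3.1.1 is more than 0.05 × 320 = 16 subjects.

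**The plan's own figures.** None is visible for the GMT ratio. The visible precision figures, the exact 95% limits for adverse event rates in SAP Table 5.5, reproduce to one decimal (for example 8/80: 4.4 to 18.8; 24/80: 20.3 to 41.3). They do not bear on the ratio.

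**Assumed inputs.** SD of log10 titer within serostatus 0.3–0.6; post-dose titers of pre-immune subjects 10-fold higher (d = 1.0 log10).

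**Does any planned contrast account for D0?**
- GMTRs (post-dose/D0) are computed within each arm; no ratio between arms is listed.
- PPAS output is defined as per-arm GMTs and percentages. SAP 5.2.4 says the main immunogenicity analyses are repeated on the PPAS, but the definition in 5.1.1.2.1.1 does not name ratios.
- The conditional subset is not produced with up to 16 such subjects. If produced, it omits D28, gives no ratio, and keeps subjects at 0.2 to <0.5 IU/mL, whom the PPAS treats as seropositive.

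So none does.

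**Shift.** With k of n pre-immune in one arm and none in the other, the ratio moves by 10^(k·d/n), up or down according to the arm. For 2 of 40: 10^(2 × 1.0/40) = 10^0.05 = 1.12. At 3.2-fold (d = 0.5) it is 1.06; at 32-fold (d = 1.5), 1.19. For 2 of 80 at 10-fold it is 1.06.

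**Shift against the SE, and CI width, 40 v 80.** SE = SD × √(1/40 + 1/80) = 0.1936 × SD. With p = 2/40, the affected arm's variance becomes SD² + p(1−p)d² = SD² + 0.0475, so the SE becomes √[(SD² + 0.0475)/40 + SD²/80].

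| SD | 95% CI with no pre-immune subjects | Shift 0.05 in SEs | CI widening (log scale) |
|---|---|---|---|
| 0.3 | ×/÷1.30 | 0.86 | 16% |
| 0.4 | ×/÷1.42 | 0.65 | 9% |
| 0.5 | ×/÷1.56 | 0.52 | 6% |
| 0.6 | ×/÷1.70 | 0.43 | 4% |

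The widening uses separate arm variances. The SAP does not say whether variances are pooled. If they are, the added variance is 39 × 0.0475/118 = 0.0157 and the widening is √(1 + 0.0157/SD²) − 1, about 2–8%.

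**After adjustment.** The shift goes and the SD returns to its within-stratum value. The cost is small: if those two were the only seropositive subjects, the contrast would rest on 38 v 80, and √(1/38 + 1/80)/√(1/40 + 1/80) = 0.1970/0.1936, an SE 1.7% larger. At SD 0.4 the CI goes from ×/÷1.47 unadjusted to about ×/÷1.43.

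**How often.** Under simple random allocation of 3, 6, 10 or 16 pre-immune subjects among 320 (20,000 draws each), a given 80 v 40 pair differs by at least 5 percentage points in pre-immune share with probability 3%, 8%, 20% and 30%. For some pair among the five arms it is 9%, 40%, 69% and 84%.

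**The case against.** The trial is descriptive. No hypothesis is tested, the sample size is called arbitrary, and randomization makes any imbalance in pre-immune subjects a chance event that the unadjusted CI already covers. The exclusions for vaccination history, blood products and rabies risk should keep such subjects few. Planned output also helps: PPAS GMTs exclude every D0-seropositive subject, so a reader can form an approximate ratio; GMTRs use each subject's own baseline; quartiles, reverse cumulative curves, boxplots and density plots would show a few very high responders. Dosage choice (Protocol 12) rests on safety and on the proportion at 0.5 IU/mL or above, the GMTs and the titer distribution; the ratios are not named there.

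All of this stands, and it limits the weight of the point. It does not close the gap, since none of these outputs is a between-group ratio with a CI that accounts for D0. A PPAS ratio formed by hand has no planned CI, and because the PPAS also drops other deviations, its difference from the FAS would not isolate baseline.

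Three stronger readings are tempting and unsupported. A reader might infer that the ratios are biased; randomization rules that out. A reader might convert the precision gain into power, perhaps through a conventional baseline correlation such as 0.5; no test is planned, no correlation is given, and that value does not suit a covariate likely to lie mostly below LLOQ. A reader might take 4 of 40 against none, a shift of 10^(4/40) = 1.26, as fairly likely because four or more of 40 has probability 0.14 at 5% pre-immune. The shift also needs none in the comparator: 0.138 × 0.95^80 = 0.002 for an 80-subject arm, or 0.138 × 0.95^40 = 0.018 for a 40-subject arm.

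**Conclusion.** The gap is real but small. Baseline RVNA is available in every subject and enters no planned between-group contrast. The effect is chance imbalance and lost precision. In the 2-of-40 example the shift stays below one SE across the assumed SDs, and the widening depends on how the variance is formed. The pre-immune count, the size of the recall response and the SD are all assumptions. If nearly all D0 titers are below LLOQ, adjusted and raw ratios will almost coincide and nothing is lost. This is a free improvement, optional in priority.

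**What to change.** In SAP 5.1.1.2.1.1, keep the raw GMT ratios on the FAS. Beside them add, for each of D14, D28 and D42, ratios and 95% CIs from one linear model on log10 titer with vaccine group and D0 serostatus (RVNA at or above LLOQ, yes/no), back-transformed, regardless of the 5% trigger. Serostatus is preferable to log10 D0 titer: most D0 values are likely to be below LLOQ, so a slope would rest on a handful of subjects, and it would depend on the computed value for results below LLOQ, which the public copy does not show in SAP 4.3.2.1. The model also supplies a CI for the six ratios not involving Imovax Rabies, for which the section describes no CI method.

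Add the D14 GMT ratios to the PPAS outputs. Limit this to D14, because the PPAS is defined at that timepoint.

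The cost is SAP wording, one model term and one more set of ratios to present; no new data are needed. It should be settled before the code is broken for the D0–D56 analysis (Protocol 6.5), so that the choice is not made after seeing results.

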5.1.2 Hypotheses and Statistical Methods for Safety Objective

5.1.2.1 Hypotheses

No hypothesis will be tested for the safety objective.

|-----------------|--|----------------|
| Post-dose 3,4,5 | | D0-D3 D4-D7 |
|-----------------|--|----------------|

- Range of number of days of occurrence categories are in Table 5.3

Table 5.3: Range of Number of Days of Occurrence Categories for Solicited Reactions during the solicited period

| | Injection Site Reactions | Systemic Reactions |
|------------------|------------------------------------|--------------------------|
| Post-dose 1 | 1 - 3 days 4 - 7 days 8 days | 1 - 3 days 4 days |
| Post-dose 2 | | 1 - 3 days 4 - 5 days |
| Post-dose 3, 4,5 | | 1 - 3 days 4 - 7 days |

Solicited reaction after any injection

“After any injection” means after the five scheduled vaccine injections, and at least after the first vaccine injection (D0).

The solicited reaction will be presented after any injections according to:

- Overall occurrence over the D0-D7 period for injection site reactions or between vaccinations for systemic reactions (up to D7 for the last 2 vaccinations)
- Time of onset period
- Intensity grade: the maximum intensity grade will be computed during the solicited period for all solicited reactions and overall for on-going solicited reactions.

30-minutes Post-Vaccination Observation Period

Unsolicited systemic AEs occurring within 30 minutes after each vaccination will be presented in summary safety tables, analyzed according to their nature (SOC and PT of the MedDRA classification) and will be listed.

Unsolicited Adverse Events

The unsolicited non-serious AEs will be analyzed

- “Between the first and the second vaccine injection”, which corresponds to AEs reported at V02 and occurring after the first vaccine injection †

† For subjects interrupting their vaccination schedule after the first injection, unsolicited AEs until 28 days after the first injection are collected at visit V02

- “Between the second and the third vaccine injection”, which corresponds to AEs reported at V03 and occurring after the second vaccine injection [†]
- “Between the third and the fourth vaccine injection”, which corresponds to AEs reported at V04 and occurring after the third vaccine injection [§]
- “Between the fourth and the fifth vaccine injection”, which corresponds to AEs reported at V05 and occurring after the fourth vaccine injection ^{**}
- “Within 28 days after the fifth vaccine injection”, which corresponds to AEs reported at V07 and occurring after the fifth vaccine injection
- “Within 28 days after any vaccine injection”, which corresponds to AEs belonging to any of the five above categories

An AE reported with an onset > 28+3 days after an injection will not be included in the analysis, but will be listed separately. The unsolicited AEs will be summarized in the safety overview and analyzed according to their nature (SOC and PT of the MedDRA classification), causality (relationship to the vaccine injection as assessed by the investigator), time of onset, duration and maximum intensity.

The occurrence of any unsolicited non-serious AE will be presented after any and each injection according to:

- *Maximum intensity:*

- Missing
- Grade 1
- Grade 2
- Grade 3

- *Time of onset categories*

- Missing
- D0-D3
- D4-D7
- D8-D14
- >=D15

[†] For subjects interrupting their vaccination schedule after the second injection, unsolicited AEs until 28 days after the second injection are collected at visit V03

[§] For subjects interrupting their vaccination schedule after the third injection, unsolicited AEs until 28 days after the first injection are collected at visit V04

^{**} For subjects interrupting their vaccination schedule after the fourth injection, unsolicited AEs until 28 days after the second injection are collected at visit V05

- *Maximum duration:*

- Missing
- 1 - 3 days
- 4 - 7 days
- 8 - 14 days
- 15 days or more

SAEs and AESIs

The SAEs and AESIs occurred during the study will be analyzed on the following periods:

1. vaccination period: after any vaccination period (D00-D56[+3D])
2. during the six-month safety follow-up period (all SAEs and AESIs from D56[+3D])

SAEs will be analyzed according to their causality (relationship to vaccine injection as assessed by the investigator), seriousness, outcome and nature (SOC and PT of the MedDRA classification).

AESIs will be summarized and analyzed according to their nature (SOC and PT of the MedDRA classification) and causality.

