- 14) Remind the subject to bring back the Diary card when they return for V02 at a specified date and time.
- 15) Remind the subject to notify the site in case of an SAE or pregnancy (for woman of childbearing potential).
- 16) Complete the relevant source document information and CRF pages for this visit.

V02 (3 days after VAC1): Collection of Safety Information and Vaccination

- 1) Review the DC1 with the subject, including any adverse events, medications, or therapy that occurred since vaccination by Investigator or delegate. The subject will continue using the DC1 to collect safety information until the V04.
- 2) Urine pregnancy test, if applicable.
- 3) Conduct a physical examination, including temperature.

- 4) Check contraindication for subsequent vaccinations (see [Section 5.2.7](#)).
- 5) Call the Interactive Response Technology (IRT) system (IV/WRS) for randomization, dose number assignment and allocation of subject number (see [Section 6.6](#)).
- 6) Inject the appropriate study vaccine (VAC2) in the opposite arm as compared to the VAC1.
- 7) Keep the subject under observation for 30 minutes, and record any adverse reaction in the source document.
- 8) Remind the subject to bring back the Diary card when they return for V03 at a specified date and time.
- 9) Remind the subject to notify the site in case of an SAE or pregnancy (for woman of childbearing potential).
- 10) Complete the relevant source document information and CRF pages for this visit.

V03 (7 [+1] days after VAC1): Collection of Safety Information and Vaccination

- 1) Review the DC1 with the subject, including any adverse events, medications, or therapy that occurred since vaccination by Investigator or delegate. The subject will continue using the DC1 to collect safety information until V04.
- 2) Urine pregnancy test, if applicable.
- 3) Conduct a physical examination, including temperature.
- 4) Check contraindication for subsequent vaccinations (see [Section 5.2.7](#)).
- 5) Call the Interactive Response Technology (IRT) system (IV/WRS) for randomization, dose number assignment and allocation of subject number (see [Section 6.6](#)).
- 6) Inject the appropriate study vaccine (VAC3) in the opposite arm as compared to the VAC2.
- 7) Keep the subject under observation for 30 minutes, and record any adverse reaction in the source document.
- 8) Remind the subject to bring back the Diary card when they return for V04 at a specified date and time.

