9.2.2 Safety Endpoints

The primary endpoint(s) for the evaluation of safety are:

- Occurrence of any unsolicited systemic adverse events (AEs) reported in the 30 minutes after each vaccine injection

Collection of injection site reactions:

- Occurrence of solicited (prelisted in the subject's diary card [DC] and electronic case report form [CRF]) injection site reactions occurring within 7 days after each injection
- Occurrence of unsolicited (spontaneously reported) injection site reactions occurring within 28 days after each injection

Collection of systemic reactions and AEs:

- Occurrence of solicited (prelisted in the subject's DC and CRF) systemic reactions between the first and the second injections as well as between the second and the third injections, and up to 7 days after the remaining injections.
- Occurrence of unsolicited (spontaneously reported) systemic AEs between each injection and up to 28 days after the last injection.
- Occurrence of serious adverse events (SAEs) throughout the trial.

Other endpoints recorded or derived will be described at the time of statistical analysis plan. Depending on the item, these could include: nature (Medical Dictionary for Regulatory Activities [MedDRA] preferred term), time of onset, duration, number of days of occurrence, grade of severity, relationship to vaccine, action taken, whether the AE led to early termination from the study, seriousness, or outcome.

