4.3 Derived Endpoints: Calculation Methods

4.3.1 Safety

Terms used in the standard safety tables to describe the safety events are specified below.

- AE: Adverse event includes immediate, solicited, and unsolicited non-serious, or serious event
- AR: Adverse reaction corresponds to related AE
- Immediate: Unsolicited systemic non-serious AE ticked “immediate (within 30 minutes from the vaccination)” by the investigator in the electronic case report form (eCRF) or SAE with time of onset within 30 minutes
- Solicited reaction: Event pre-listed in the eCRF, and which occurred during the solicited period
- Unsolicited AE: AE recorded in the eCRF as unsolicited or SAE forms, excluding solicited reaction. Therefore, include immediate AE.

Unsolicited non-serious injection site reactions are always recorded without relationship and analyzed as ARs.

Unsolicited AEs analyzed are AEs up to 28 days +3 days after vaccination. Unsolicited AEs occurring after the defined period - and which are not SAEs - will be presented in a separate listing.

- SAE: Unsolicited AE considered serious by the investigator (reconciled with Global Pharmacovigilance database)
- Adverse event of specific interest (AESI): the list of Medical Dictionary for Regulatory Activities (MedDRA) preferred terms (PT) defined in the protocol to select these AEs in the database:
 - Anaphylactic reaction (PT)
 - Encephalitis (PT)

- Convulsion (PT)

4.3.1.1 **Solicited Reactions**

4.3.1.1.1 **Daily Intensity**

All daily records for solicited reactions will be derived into daily intensity according to the following classification: None, Grade 1, Grade 2, Grade 3, or Missing.

For the derivation of daily intensities the following sequential steps will be applied:

1) For solicited reactions (except for fever) with an Investigator presence recorded as "No" and with all daily records missing, all daily intensities will be derived as "None."

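### Two SAP footnotes name the wrong anchor injection for unsolicited non-serious AEs in subjects who stop after dose 3 or dose 4, contradicting the 28-day rule elsewhere

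*SAP*

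**What the plan says.** SAP 5.1.2.2.1, under Unsolicited Adverse Events, analyses unsolicited non-serious AEs by inter-injection interval, with one footnote per interval for subjects who stop early. The four footnotes read:

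- Stop after dose 1: "For subjects interrupting their vaccination schedule after the first injection, unsolicited AEs until 28 days after the first injection are collected at visit V02".
- Stop after dose 2: "For subjects interrupting their vaccination schedule after the second injection, unsolicited AEs until 28 days after the second injection are collected at visit V03".
- Stop after dose 3 (§): "For subjects interrupting their vaccination schedule after the third injection, unsolicited AEs until 28 days after the first injection are collected at visit V04".
- Stop after dose 4 (double asterisk), in part: "after the fourth injection, unsolicited AEs until 28 days after the second injection are collected at visit V05".

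The general rule is stated in several other places:

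- Protocol 9.2.2 lists as an endpoint: "Occurrence of unsolicited (spontaneously reported) systemic AEs between each injection and up to 28 days after the last injection". Protocol 9.2.3.3 gives the same period for diary recording.
- SAP 4.3.1 says: "Unsolicited AEs analyzed are AEs up to 28 days +3 days after vaccination".
- The main text of SAP 5.1.2.2.1 presents unsolicited events to 28 days after the last injection. Just above the footnotes it sends an event to a separate listing only when onset is more than 28+3 days after an injection.

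For unsolicited events, the SAP takes as denominator all subjects vaccinated at the dose, or all vaccinated at least once for the analysis after any dose.

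**The concern.** The first two footnotes count from the last injection received. The last two count from an earlier one, and neither document gives a reason. Someone who followed § and the double-asterisk footnote literally would apply a shorter post-dose window to subjects stopping after dose 3 or dose 4 than both documents set elsewhere.

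These subjects are counted as fully observed in the denominator, so an event that was not captured would be read as no event. The affected result is the summary of unsolicited non-serious AEs within 28 days of any injection, which is defined as the union of the interval categories that carry the footnotes. The loss would fall in the SAP's latest onset category (day 15 or later).

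**Working it through.** **Inputs**

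- Injections are "administered at D0, D3, D7, D14 and D28" (SAP 3.1), so doses 1 to 4 fall on days 0, 3, 7 and 14.
- The anchor injection for each case comes from the four footnotes.
- The reference window is 28 days after the last injection (Protocol 9.2.2), with +3 days for analysis (SAP 4.3.1).

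**Formula**

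Days covered after the last dose = (day of anchor injection + 28) − (day of last injection received).

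| Stops after | Anchor in footnote | Window ends | Days after last dose | Short of 28 | End if anchored on last dose |
|---|---|---|---|---|---|
| Dose 1 | Injection 1 | 0+28 = D28 | 28−0 = 28 | 0 | D28 |
| Dose 2 | Injection 2 | 3+28 = D31 | 31−3 = 28 | 0 | D31 |
| Dose 3 (§) | Injection 1 | 0+28 = D28 | 28−7 = 21 | 7 (7/28 = 25%) | 7+28 = D35 |
| Dose 4 (double asterisk) | Injection 2 | 3+28 = D31 | 31−14 = 17 | 11 (11/28 = 39%) | 14+28 = D42 |

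The first two footnotes reproduce the 28-day rule and the last two do not.

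**Sensitivity to visit windows**

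- The protocol allows dose 3 on D7 or D8: "V03 (7 [+1] days after VAC1): Collection of Safety Information and Vaccination". Footnote § then covers 28−8 = 20 to 28−7 = 21 days. The SAP's Table 3.2 gives D7 ±1, which makes it 20 to 22.
- With dose 4 on D13 to D15 and dose 2 on D3, the double-asterisk footnote covers 31−15 = 16 to 31−13 = 18 days.
- Adding the 3-day tolerance to the nominal figures gives 21+3 = 24 and 17+3 = 20 days, against 28+3 = 31.

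**Where the loss falls**

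The missing days are 22–28 after dose 3 and 18–28 after dose 4. All lie in the onset category from day 15 upward. Of the 14 days from 15 to 28, 7 are lost under § and 11 under the double-asterisk footnote.

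**A case the SAP does not settle**

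Take an event on D33 in a subject who stopped after dose 3. Onset is 33−7 = 26 days after the last dose, so the 28+3 rule includes it. Footnote § ends at D28 and does not.

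**Effect on rates**

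This cannot be computed, because the documents give no expected number of subjects stopping after dose 3 or dose 4. As a scale, one subject whose only unsolicited non-serious event is missed lowers a group's rate by 1/80 = 1.25 percentage points in a VRVg-2 group, or 1/40 = 2.5 points in the VRVg-1 or Imovax Rabies group, if all are vaccinated.

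**The case against.** The strongest reply is that this is a slip with little practical force, and much of that reply stands.

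- **Collection is governed by the protocol.** Protocol 9.2.2 and 9.2.3.3 set 28 days after the last injection. Protocol 5.2.7.2 keeps contraindicated subjects in safety follow-up, and 5.2.11 continues scheduled safety follow-up after most early terminations. A reader might infer that sites stop recording events early. The documents do not show that, and nothing suggests that sites work from SAP footnotes.
- **The footnotes can be read as stating which visit page carries the events.** The only explicit exclusion rule, onset beyond 28+3 days, is correct and sits in the same subsection. That limits the effect, but the two footnotes still state an end point that conflicts with it, and the SAP does not say which prevails.
- **Serious events are not at stake.** Since vaccination is stopped for related SAEs, significant allergic reactions or Guillain-Barré syndrome, a reader might infer that the most important late events are lost. They are not. The footnoted categories cover unsolicited non-serious AEs only. SAEs and AESIs are collected to six months after the last vaccination (Protocol 5.1.1, 9.2.3.4 and 9.2.3.5).
- **The per-interval rows are not short of follow-up relative to other subjects.** Those who continue contribute about 14−7 = 7 days between doses 3 and 4, and 28−14 = 14 days between doses 4 and 5. Even read literally, stoppers contribute 21 and 17. The shortfall exists only against 28 days after the stopper's own last dose, so it matters for the summary after any injection.

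The contradiction itself is not answered by any of this.

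**Conclusion.** The point holds as an internal inconsistency in the SAP. Footnote § and the double-asterisk footnote give 21 and 17 days after the last dose on the nominal schedule, where Protocol 9.2.2, SAP 4.3.1 and the rest of SAP 5.1.2.2.1 give 28 (+3). The anchors run first, second, first, second, which suggests that the first pair was copied and not updated. A reader might take the shorter windows as a deliberate design choice, but neither document presents them as one.

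The possible consequence is under-counting of non-serious events with onset at day 15 or later, in the summary after any injection, among subjects who stop exactly after dose 3 or dose 4. That rests on two assumptions: that the footnotes are applied literally in place of the 28+3 rule, and that such subjects exist. Their number is unstated and probably small, and the analysis is descriptive. It is worth correcting because it is a stated analysis rule that gives the wrong window if followed.

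**What to change.** In SAP 5.1.2.2.1, reconcile the two footnotes with the protocol's 28-day rule. Anchor § on the third injection and the double-asterisk footnote on the fourth, so that all four count from the last injection received. The nominal windows then end at D35 and D42. A single sentence covering all early stoppers would do the same job and could not drift out of step.

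The cost is two words in the SAP. Endpoints, denominators, sample size and the protocol are unchanged. It would be sensible to confirm that the CRF completion guidelines use the same anchor; they are not among the documents reviewed, and no mismatch in them is alleged.
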